2 STUDY DESCRIPTION

[figure not shown]
2.1 Study Design

This is an open-label, randomized phase IIIb/IV dose frequency optimization trial in adult patients with advanced/metastatic (Stage IIIb/IV) NSCLC (non-Sq and Sq). Subjects will have received approximately up to 12 months (52 weeks) of nivolumab therapy at either 3 mg/kg or 240 mg every 2 weeks and achieved a complete response (CR), partial response (PR), or stable disease (SD) as evidenced by 2 consecutive tumor assessments prior to enrollment. At enrollment, subjects will be randomized 1:1 to receive either 240 mg every 2 weeks (Arm 1) or 480 mg every 4 weeks (Arm 2). Randomization will be stratified by histology (Sq vs. Non-Sq) and response criteria to pre-study nivolumab at randomization (CR or PR vs. SD). For subjects receiving nivolumab 240 mg every 2 weeks, each 14-day dosing period will constitute a cycle. For subjects receiving nivolumab 480 mg every 4 weeks, each 28-day dosing period will constitute a cycle.

Subjects will continue treatment until disease progression or unacceptable toxicity for a maximum of 2 years from first randomized dose. The follow-up period begins when the decision to permanently discontinue a subject from study therapy is made (no further treatment or retreatment with nivolumab is anticipated). All subjects who discontinue study drug should comply with protocol specified follow-up procedures as outlined in Section 5 of the Clinical Protocol until death or the conclusion of the study. The only exception to this requirement is when a subject withdraws consent for all study procedures including post-treatment study follow-up or loses the ability to consent freely.

The study design schematic is presented in [Figure 2.1-1](#).

Figure 2.1-1: Study Schema

Each patient’s last study visit will be defined as the last on-treatment or follow-up visit that occurs prior to the date of 3 years after the initiation of randomized therapy. The study will be completed no later than 3 years after the last subject’s first visit.

2.2 Treatment Assignment

CA209384 is a randomized study. After the subject’s eligibility is established and informed consent has been obtained, the subject will be enrolled, and a number will be assigned through an interactive web-based response system (IWRS). Specific instructions for enrollment and randomization procedures using IWRS will be provided to the investigational site in a separate document/manual. Required information for registration includes but is not limited to the following:

- Response at randomization (CR or PR vs. SD)
- Tumour histology (Sq vs. Non-Sq)

Patients meeting all eligibility will be randomized to 1 of the 2 treatment arms. Randomization will be stratified by the following factors:

- Histology (Sq vs. Non-Sq)

- Response at randomization (CR or PR vs. SD)

2.3 Blinding and Unblinding

Not applicable. This is an open-label study.

2.4 Protocol Amendments

There are currently 4 approved amendments. Table 2.4-1 shows the history of protocol amendment.

Document	Date	Summary of Changes
Amendment 1	11-Dec-2015	
 1. To allow the inclusion of subjects who are ineligible for or refuse chemotherapy in the first-line advanced non-small cell lung cancer setting and to use the flat dose instead of the weighted dose. 2. Human Immunodeficiency Virus testing at screening was also added for Germany sites only.
Revised Protocol 01	11-Dec-2015	Incorporates Amendment 01
Amendment 2	12-Feb-2016	Change the Human Immunodeficiency Virus criterion to reflect the language that is used across the nivolumab clinical development program and adjusted the frequency of magnetic resonance imaging scans in those with a history of brain metastasis to align with study assessments.
Revised Protocol 02	12-Feb-2016	Incorporates Amendment 02
Amendment 4	12-Aug-2016	
 1. Change the pre-study nivolumab requirement 2. Add a small increase to the sample size 3. Add immunogenicity as an endpoint 4. Make small changes to the laboratory and tumor assessments and duration of contraception use to align the protocol with updates to the nivolumab clinical development program.
Revised Protocol 03	12-Aug-2016	Incorporates Amendment 04
Revised Protocol 04	09-Feb-2018	
 1. Included additional language for nivolumab program level updates 2. Added information for interim analysis
Revised Protocol 05	26-Jun-2018	
 1. Reduced sample size and modified primary endpoint from non-inferiority to one-sided confidence interval around the differences of PFS rates. 2. Modified follow-up for overall survival for 3 years. 3. Added rationale for maximum treatment duration with nivolumab of 2 years.

2.5 Data Monitoring Committee

A Data Monitoring Committee (DMC) will be established to provide oversight of safety and efficacy (including assessment of 6 month PFS co-primary endpoint) considerations and to provide advice regarding actions the committee deems necessary for the continuing protection of enrolled patients and those yet to be recruited to the trial as well as for the continuing validity and scientific merit of the study results. The DMC is charged with assessing such actions in light of an acceptable benefit/risk profile for nivolumab.

One safety interim review will be conducted after 25 patients per treatment arm reach at least 3 months of treatment exposure after randomization. The DMC will review all available safety data and any available efficacy data that is provided. These efficacy data will be provided to allow evaluation of safety in the context of benefit. One formal interim review will be conducted at minimum of 6 months after the last patient's first visit. The DMC will review the analysis for 6-month PFS and OS as well as the safety data. In addition, it is anticipated that the DMC will meet at every 12 months or more frequently if deemed necessary for the duration of the trial to perform safety assessments.

3 OBJECTIVES

3.1 Primary

The coprimary objectives are to compare the PFS rate at 6 months after randomization and PFS rate at 1 year after randomization, as measured by investigator-assessed response using Response Evaluation Criteria in Solid Tumor (RECIST) 1.1 criteria, of nivolumab 240 mg every 2 weeks (Arm 1) and nivolumab 480 mg every 4 weeks (Arm 2) in subjects with advanced/metastatic (Stage IIIb/IV) NSCLC (non-Sq and Sq).

3.2 Secondary

The secondary objectives are:

- To compare PFS rate in Arms 1 and 2 at 1 year after randomization by tumor histology and by response criteria before randomization.
- To compare PFS rate at 2 years after randomization in Arms 1 and 2.
- To compare the OS rate at 1 year after randomization and up to 3 years after randomization in Arms 1 and 2, in all treated subjects, by tumor histology, and by response criteria before randomization.
- To assess safety and tolerability of nivolumab, as measured by the incidence and severity of AEs and specific laboratory abnormalities, in all treated subjects, in Arms 1 and 2, by tumor histology, and response criteria before randomization.

[REDACTED]

[REDACTED]

[REDACTED]

4 ENDPOINTS

4.1 Primary Endpoints

The coprimary endpoints of this trial will be assessed by PFS rate at 6 months after randomization and PFS rate at 1 year after randomization. PFS is defined as the time from the date of randomization to the date of first documented tumor progression determined by the investigator using RECIST 1.1 criteria or death due to any cause, whichever is earlier. Subjects who do not progress or die will be censored on the date of their last evaluable tumor assessment. Clinical deterioration in the absence of unequivocal evidence of progression (per RECIST 1.1) is not considered progression for purposes of determining PFS. Subjects who die without a reported prior progression will be considered to have progressed on the date of their death. Subjects who do not have any on-study tumor assessments and do not die will be censored on the date of randomization. Subjects who receive any subsequent anti-cancer therapy (including on-treatment palliative radio therapy [RT] of non-target bone lesions or central nervous system [CNS] lesions) without a prior reported progression will be censored at the last evaluable tumor assessment prior to or on the date of initiation of the subsequent anti-cancer therapy.

Table 4.1-1: Censoring Scheme for Primary Definition of PFS

Situation	Date of Progression or Censoring	Outcome
No baseline tumor assessments and no death	Randomization	Censored
No on study tumor assessments and no death	Randomization	Censored
New anticancer treatment started without a prior reported progression per RECIST 1.1 or death	Date of last evaluable tumor assessment prior to or on the date of initiation of the subsequent anti-cancer therapy	Censored
Progression per RECIST 1.1 documented at scheduled or unscheduled visit and no new anticancer treatment started before	Date of the first documented tumor progression	Progressed
Subject progression free (per RECIST 1.1) and no new anticancer treatment started	Date of last tumor assessment	Censored
Death without prior progression per RECIST 1.1 and no new anticancer treatment started	Date of death	Progressed

RECIST: Response Evaluation Criteria in Solid Tumors

[figure not shown]
PFS rate at 6 months is the rate from Kaplan-Meier estimate 6 months after randomization; PFS rate at 1 year is the rate from Kaplan-Meier estimate at 1 year after randomization.

4.2 Secondary Endpoints

- PFS rate at 1 year after randomization by tumor histology (Sq vs. Non-Sq) and RECIST v1.1 response (CR or PR vs. SD) assessed before randomization
- PFS rate at 2 years after randomization
- OS rate at 1 year and OS rate up to 3 years after randomization by arm, tumor histology, and RECIST v1.1 response status at randomization (CR or PR vs. SD). OS is defined as time from the date of randomization to the date of death. Patients who did not die by the end of the study will be censored at the last known date alive. OS rate at 1 year is the rate from Kaplan-Meier estimated at one year after randomization.
- Safety and tolerability of nivolumab, as measured by incidence and severity of AEs and specific laboratory abnormalities.

Safety endpoints include adverse events (AEs), serious adverse events (SAEs), AEs leading to discontinuation, AEs leading to dose delay, immune-mediated adverse events (IMAEs), select adverse events (select AEs), other events of special interest, and deaths. Adverse events will be coded and grouped into Preferred Terms (PT) by System Organ Class (SOC), using the most current version of Medical Dictionary for Regulatory Activities (MedDRA). The intensity of AEs will be graded 1 to 5 according to the National Cancer Institute Common Terminology Criteria for Adverse Events (CTCAE) Version 4.0. The use of immune modulating concomitant medication will be also summarized. In addition specific clinical laboratory tests and vital signs will be analyzed.

[REDACTED]

5 SAMPLE SIZE AND POWER

The primary analyses evaluate the non-inferiority of post-randomization 6-month and 12-month milestone PFS rate of nivolumab 480 mg Q4W vs the PFS rate of nivolumab 240 mg Q2W in subjects with disease control (CR/PR/SD) after approximately up to 12 months (52 weeks) of nivolumab 3 mg/kg or 240 mg Q2W treatment. The non-inferiority margin of -10% was chosen for this study. Patients who received nivolumab for up to 12 months (52 weeks) and achieved CR, PR, or SD confirmed by 2 consecutive tumor assessments in the pre-study period will be randomized. Study CA209017 and CA209057 were used for estimating PFS rate at 6 months and 12 months. Patients who are either CR, PR or SD between months 3 and 12 were selected and their 6 month and 12 month PFS rate were estimated: the 12-month milestone PFS rate post-randomization is 0.48 with 240 mg Q2W and 6-month PFS rate post-randomization is 0.63.

The sample size was computed based on a cumulative hazard function which account for both progression and censoring distributions. Using cumulative hazard function and its relation with survival function, it is estimated that approximately 620 patients, 310 in each arm, will provide 80% power for the lower bound of a 95.2% one-sided confidence interval above -10% at the 12 month milestone and the lower bound of a 99.3% confidence interval above -10% at 6 months if PFS rates of the 2 arms are assumed to be equal. The experiment-wise error rate is maintained at one-sided 5% level.

To account for those who are randomized but do not receive treatment, 320 subjects per arm will be randomized. With a 15% screen failure rate, approximately 753 subjects will be screened to achieve approximately 640 randomized subjects.

Due to early stop of enrollment of the study, the sample size will be the number of subjects randomized after enrollment stops. Approximately 350 subjects are expected to be randomized and receive study treatment. With the significant reduction of sample size, there is insufficient power to demonstrate non-inferiority of the two treatment regimens. Hence, the adjustment of alpha between 6 months and 12 months PFS rates (as originally planned) will not be conducted. Instead, 95% one-sided confidence interval around the difference of PFS rates will be generated.

6 STUDY PERIODS, TREATMENT REGIMENS AND POPULATIONS FOR ANALYSES

6.1 Study Periods

6.1.1 Baseline period

Baseline evaluations or events will be defined as evaluations or events that occur before the date and time of the first dose of study treatment (or randomization date).

In cases where the time (onset time of event or evaluation time and dosing time) is missing or not collected, the following definitions will apply:

- Pre-treatment AEs will be defined as AEs with an onset date prior to but not including the day of the first dose of study treatment
- Baseline evaluations (physical examination, Eastern Cooperative Oncology Group (ECOG) Performance Status, laboratory tests and vital signs) will be defined as evaluations with a date (and time if collected) on or prior to the day (and the time if collected) of first dose of study treatment

If there are multiple valid assessments, the assessment that is closest to day (and time if collected) of the first dose of study treatment (or randomization date) will be used as the baseline in the analyses. If multiple assessments are collected at the same date (and time if collected), the assessment with the latest database entry date (and time if collected) will be considered as baseline.

6.1.2 Post baseline period

On-treatment AEs will be defined as AEs with an onset date-time on or after the date-time of the first dose of study treatment (or with an onset date on or after the day of first dose of study treatment if time is not collected or is missing). For subjects who are off study treatment, AEs will be counted as on-treatment if the events occurred within 100 days of the last dose of study treatment, unless otherwise specified.

On-treatment evaluations (laboratory tests, pulse oximetry and vital signs) will be defined as evaluations taken after the day (and time, if collected and not missing) of first dose of study treatment. For subjects who are off study treatment, evaluations should be within 100 days of the last dose of study treatment.

Post-treatment AEs will be defined as AEs with an onset date-time 100 days after last dose of study treatment.

Late emergent drug related AEs will be defined as drug related AEs with an onset date greater than 100 days after the last dose of study treatment in subjects off study treatment.

Post-treatment evaluations, if necessary, will be defined as evaluations taken 100 days after last dose of study treatment.

6.2 Treatment Regimens

The treatment group “**as randomized**” will be retrieved from the IWRS system

- Arm 1: nivolumab administered intravenously as a 30-minute (\pm 5 minutes) IV infusion on Day 1 of each treatment cycle at 240 mg every 2 weeks, until progression, unacceptable toxicity, withdrawal of consent, or the patient reaches a maximum of 5 years of treatment from the first on-study dose, or the study ends, whichever occurs first.
- Arm 2: nivolumab administered intravenously as a 30-minute (\pm 5 minutes) IV infusion on Day 1 of each treatment cycle at 480 mg every 4 weeks, until progression, unacceptable toxicity, withdrawal of consent, or the patients reaches a maximum of 5 years of treatment from the first on-study dose, or the study ends, whichever occurs first.

The treatment group “**as treated**” will be the same as the arm randomized by IWRS. However, if a subject receives the incorrect drug for **the entire period** of treatment, the subject’s treatment group will be defined as the incorrect drug the subject actually received.

6.3 Populations for Analyses

- All enrolled subjects: All subjects who sign an informed consent form and are registered into the IWRS.
- All randomized subjects: All enrolled subjects who are randomized to 240 mg every 2 weeks or 480 mg every 4 weeks. This is the primary population for efficacy analyses. Analyses of demography and baseline characteristics, as well as outcome research, will be performed on this population, grouped as randomized.
- Per-protocol subjects: All randomized subjects who have no major protocol deviations. The relevant protocol deviations include the programmable deviations from inclusion and exclusion criteria at study entrance and administration of prohibited medications during the study. Non-programmable relevant eligibility and on-treatment protocol deviations, as well as significant (both programmable and non-programmable) eligibility including those subjects with untreated, symptomatic CNS metastases who should be excluded and on-treatment protocol deviations will be reported through a PPD tracking system - Clinical Trial Management System (CTMS). The details of relevant protocol deviations are described in [Section 7.2.2](#). The primary efficacy endpoint will be analyzed for this population as a sensitivity analysis.
- All treated subjects: All randomized subjects who receive at least 1 dose of nivolumab. This is primary population for safety analyses.

- 

7 STATISTICAL ANALYSES

The following sections describe the statistical analyses in the study.

7.1 General Methods

Discrete variables will be summarized with the number and proportion of subjects falling into each category, grouped by treatment arm (with total). Percentages given in these tables will be rounded and therefore, may not always sum to 100%. Continuous variables will be summarized

using the mean, standard deviation (SD), median, minimum and maximum values (summary statistics) by treatment arm (with total). Corresponding by-subject listings will also be created for appropriate populations.

Time to event distribution (i.e. PFS and OS) will be estimated using Kaplan-Meier product-limit techniques. Median survival time along with two-sided 95% confidence interval (CI) will be constructed using Brookmeyer and Crowley method for each treatment arm. Rates at fixed time points (i.e. PFS at 6 months) will be derived from the Kaplan-Meier estimate and corresponding two-sided 95% confidence intervals will be derived for each treatment arm along with one-sided 95% CI for the difference between treatment arms based on Greenwood formula.

The stratified hazard ratio between the 2 treatment arms along with CI will be obtained by fitting a stratified Cox proportional hazard model with the treatment arm variable and stratification factors (tumour histology [Sq. vs. Non-Sq.] and response status at randomization [CR or PR vs. SD]).

Statistical analyses will be carried out using SAS software (SAS Institute, Cary, North Carolina, USA), unless otherwise noted.

7.2 Study Conduct

7.2.1 Accrual

The following will be summarized for all enrolled subjects:

- Number of subjects accrued by country and investigational site
- Number of subjects accrued by month.

A by-subject listing of accrual will be produced.

7.2.2 Relevant Protocol Deviations

The relevant protocol deviations will be summarized for all randomized subjects, by treatment arm and total. The following programmable deviations from inclusion and exclusion criteria will be considered as relevant protocol deviations. Non-programmable relevant eligibility and on-treatment protocol deviations, as well as significant (both programmable and non-programmable) eligibility including those subjects with untreated, symptomatic CNS metastases who will be excluded and on-treatment protocol deviations will be reported.

Eligibility at entrance:

- Subjects without histologically or cytological documented Sq.- or non-SqNSCLC who present with Stage IIIB/IV disease
- Subjects had received and tolerated nivolumab 3 mg/kg or 240 mg every 2 weeks for more than 12 months
- Subjects without at least 2 consecutive tumor assessments confirming CR, PR, or SD to the pre-study nivolumab treatment (latest scan must be performed within 28 days prior to randomization)

- Subjects without measurable disease by computed tomography (CT) or magnetic resonance imaging (MRI) per RECIST 1.1 criteria at the time of starting the first dose of pre-study nivolumab treatment
- Subject with baseline ECOG performance status > 2

On-Study:

- Subjects receiving concurrent antineoplastic therapy (i.e., chemotherapy, hormonal therapy, immunotherapy, extensive, non-palliative radiation therapy, or standard or investigational agents for treatment of NSCLC)
- Subjects receiving immunosuppressive agents.
- Subjects receiving immunosuppressive doses of systemic corticosteroids (except as stated in the Clinical Protocol Section 3.4.3).
- Subjects receiving treatment other than the randomized treatment

A by-subject listing of relevant protocol deviations will also be produced.

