##### **2. Target Population**

- a) Subjects with histologically or cytologically documented Sq- or non-SqNSCLC who present with Stage IIIB/Stage IV disease (according to version 7 of the International Association for the Study of Lung Cancer Staging Manual in Thoracic Oncology), or with recurrent or progressive disease following multimodal therapy (radiation therapy, surgical resection, or definitive chemoradiotherapy for locally advanced disease).
- b) Subjects must have received and tolerated nivolumab 3 mg/kg or 240 mg every 2 weeks for up to 12 months (52 weeks). Subjects may continue to receive pre-study nivolumab treatment during screening assessments as noted in [Table 5.1-2](#).
- c) Subjects must have at least 2 consecutive tumor assessments confirming CR, PR, or SD to the pre-study nivolumab treatment (latest scan must be performed within 28 days prior to randomization).
- d) Subjects must have had measurable disease by CT or MRI per RECIST 1.1 criteria at the time of starting first dose of pre-study nivolumab treatment.
- e) As of Amendment 01, this criterion is no longer applicable.
  - i) As of Amendment 01, this criterion is no longer applicable.
  - ii) As of Amendment 01, this criterion is no longer applicable.
  - iii) As of Amendment 01, this criterion is no longer applicable.
  - iv) As of Amendment 01, this criterion is no longer applicable.
  - v) Subjects with a known activating EGFR mutation or ALK translocation are eligible if they have received an EGFR or ALK TKI in addition to a platinum-based chemotherapy
  - vi) As of Amendment 01, this criterion is no longer applicable.
- f) ECOG PS 0-2
- g) Subjects with stable CNS metastases are eligible if CNS metastases are treated and subjects have neurologically returned to baseline (except for residual signs or symptoms related to the CNS treatment) for at least 2 weeks prior to enrollment. In addition,

subjects must be either off corticosteroids or on a stable or decreasing dose of  $\leq 10$  mg daily prednisone (or equivalent).

h) All baseline laboratory requirements will be assessed and should be obtained within 14 days (unless otherwise specified in [Table 5.1-1](#)) of first dose of randomized nivolumab. Screening laboratory values must meet the following criteria:

- i) WBCs  $\geq 2000/\mu\text{L}$
- ii) Neutrophils  $\geq 1500/\mu\text{L}$
- iii) Platelets  $\geq 100 \times 10^3/\mu\text{L}$
- iv) Hemoglobin  $\geq 9.0$  g/dL

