7.3.2 Demographics and Other Baseline Characteristics

Descriptive statistics will be used to summarize the following demographics and baseline characteristics for all randomized subjects, as well as for per-protocol subjects, by treatment arm and total.

- Age (years)
- Age group (< 65, ≥ 65 - < 75, ≥ 75, ≥ 65)
- Gender, Race/Ethnicity, Region/ Country
- ECOG PS (0, 1, 2)
- Baseline weight (kg), height (cm)

- Baseline body mass index (BMI) (kg/m^2), which is calculated as (body weight in kilograms) / (height in meters)²
- Tumor histology (Sq/Non-Sq)
- Disease stage at initial diagnosis (Stage 0/IA/IB/IIA/IIB/IIIA/IIIB/IV)
- Time from initial disease diagnosis to randomization (< 1 year, 1-< 2 year, 2 - < 3 year, 3 -< 4 year, 4 - < 5 year, \geq 5 year)
- Cell type (Adenocarcinoma, Squamous Cell Carcinoma, Large Cell Carcinoma, Broncho-alveolar Carcinoma, Other)
- EGFR mutation status, ALK translocation status
- Tobacco use (current, former, never, unknown)
- All lesions (investigator tumor assessments at baseline): sites of disease, number of disease sites per subject
- Target lesions (investigator tumor assessments at baseline): presence of target lesions, site of target lesion, sum of diameters of target lesions.

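### SAP 7.2.2 turns inclusion criterion 2a into a deviation rule that keeps only the Stage IIIB/IV route, so some eligible subjects can be counted as deviations and left out of the per-protocol PFS analysis

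*SAP*

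**What the plan says.** **Entry.** Protocol 3.3.1, criterion 2a (repeated in the synopsis), gives two alternatives. The first is "Subjects with histologically or cytologically documented Sq- or non-SqNSCLC who present with Stage IIIB/Stage IV disease". The second is "or with recurrent or progressive disease following multimodal therapy (radiation therapy, surgical resection, or definitive chemoradiotherapy for locally advanced disease". Either is enough.

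**Deviation rule.** SAP 7.2.2 introduces its list with "The following programmable deviations from inclusion and exclusion criteria will be considered as relevant protocol deviations". The first item under eligibility at entrance is "Subjects without histologically or cytological documented Sq.- or non-SqNSCLC who present with Stage IIIB/IV disease". The recurrent or progressive alternative does not appear there, and nothing else in the SAP restores it.

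**Link to an analysis set.** SAP 6.3 has "Per-protocol subjects: All randomized subjects who have no major protocol deviations" and then "The relevant protocol deviations include the programmable deviations from inclusion and exclusion criteria at study entrance", and sends the reader to 7.2.2 for details. SAP 7.5.3 repeats the PFS analyses of 7.5.1 in this set, and SAP 7.3.2 produces baseline tables for it.

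**Stage data.** The one stage variable that the SAP lists is "Disease stage at initial diagnosis (Stage 0/IA/IB/IIA/IIB/IIIA/IIIB/IV") in 7.3.2. The SAP names no variable for stage at study entry and none for recurrence.

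**The concern.** A per-protocol set should remove subjects who broke the rules. Here the rule that defines a breach is narrower than the entry criterion it stands for, so a subject can satisfy criterion 2a and still be reported as an eligibility deviation.

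Two outputs are exposed. The deviation summary and by-subject listing would show breaches that did not occur. The per-protocol PFS rates would leave out some subjects because of their disease history and not because of non-adherence. A gap between the all-randomized and per-protocol results could then partly reflect case mix, which weakens the sensitivity analysis as a check on adherence.

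**Working it through.** The plan states no figure on this point, so the check is mainly a comparison of texts.

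**1. Criterion against rule.**

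| Element of 2a | Protocol 3.3.1 | SAP 7.2.2 |
|---|---|---|
| Documented Sq or non-Sq NSCLC | yes | yes |
| Stage IIIB/IV | yes, route one | yes |
| Recurrent or progressive after multimodal therapy | yes, route two | absent |

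Neighbouring items keep their detail: the tumor-assessment item retains the 28-day limit, and the corticosteroid item retains its exception by reference to Protocol 3.4.3. Among these items, only 2a loses a qualifying alternative.

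**2. Who is exposed.** Take a subject resected at Stage II who later recurred and then had disease control on nivolumab.

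- Under 2a, the subject is eligible by route two.
- Under 7.2.2, if the rule uses stage at entry and the recurrence is recorded as Stage IV, the subject passes.
- Under 7.2.2, if the recorded stage is anything else, or if the rule uses stage at initial diagnosis, the subject is flagged.

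The exposed group is therefore second-route subjects not recorded as Stage IIIB/IV. SAP 7.3.4 tabulates adjuvant, neo-adjuvant and locally advanced settings of prior therapy, so subjects who began with earlier disease were foreseen. Their number is not given.

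**3. From flag to exclusion.** 7.2.2 makes the item a relevant deviation. 6.3 excludes subjects with major deviations, describes the relevant ones in its next sentence and cites 7.2.2. 7.5.3 then runs PFS without them.

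**4. Illustration of lost precision.** Inputs: about 350 subjects randomized 1:1 (SAP 5), and planning PFS rates of 0.48 at 12 months and 0.63 at 6 months (SAP 5). The same rate is taken in both arms, with binomial variance and no censoring before the time point. The distance from the estimated difference to its one-sided 95% lower bound is

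d = 1.645 × √(2p(1 − p)/n), with n per arm.

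At 12 months:

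- Nobody removed, n = 175: √(2 × 0.48 × 0.52/175) = 0.0534, so d = 8.8 points.
- 10% removed, n = 157.5: √(0.4992/157.5) = 0.0563, so d = 9.3 points.

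The share removed is an assumption. Over a range of shares:

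| Assumed share removed | Subjects of 350 | d at 12 months (points) | d at 6 months (points) |
|---|---|---|---|
| 0% | 0 | 8.79 | 8.49 |
| 5% | 17.5 | 9.01 | 8.71 |
| 10% | 35 | 9.26 | 8.95 |
| 20% | 70 | 9.82 | 9.49 |
| 30% | 105 | 10.50 | 10.15 |

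The table shows what losing any such share would cost. It does not estimate how many subjects the rule affects.

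**The case against.** **The bullet can be read another way.** Taken literally, *without* may govern only the documented NSCLC, in which case a recurrent subject with confirmed histology lacks nothing that the item names. This is fair, but on that reading the stage part of 2a is not checked at all. The wording needs correcting either way.

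**The data field is unknown.** A reader might infer that the rule is programmed from stage at initial diagnosis, so that everyone first diagnosed below Stage IIIB is dropped. The documents do not say so. The variable in 7.3.2 belongs to a list of baseline summaries, and neither the CRF nor the programming specification is in the documents. The item stands under eligibility at entrance, and both documents describe the population as Stage IIIB/IV. This objection stands. Using initial stage is a risk, because no other stage variable is listed, but it is not an established fact.

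**The step to the per-protocol set is not explicit.** 6.3 uses *major* and then *relevant* without equating them. The cross-reference to 7.2.2 makes the link the natural reading, though not a certain one.

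**Little depends on this set.** The primary efficacy population is all randomized subjects. Non-inferiority is no longer a goal after Revised Protocol 05, and per-protocol PFS is one of several sensitivity analyses with no decision rule attached. Disease history is fixed before 1:1 randomization, so the exclusion is balanced between arms in expectation. The SAP's own baseline tables for both populations would show some of any case-mix shift. All of this stands and limits the consequence.

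**Conclusion.** The omission is real. On its natural reading, 7.2.2 counts an eligible second-route subject not recorded as Stage IIIB/IV as a deviation, and 6.3 then removes that subject from the per-protocol PFS analysis. This rests on two readings: that the item tests stage, and that the relevant deviations of 7.2.2 are the major deviations of 6.3.

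The effect is confined to the deviation summary and listing, the per-protocol baseline tables and the per-protocol sensitivity analysis. There it means an inflated deviation count, a possible case-mix shift and some lost precision. The all-randomized co-primary analysis is unaffected, and no between-arm bias is expected.

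The size is unknown. A reader might infer that 35 to 105 subjects (10% to 30% of 350) are wrongly excluded, or that the whole group with recurrent disease disappears. The documents support neither: they give no count of second-route subjects, and those recorded as Stage IIIB/IV would pass. The widening from about 8.8 to 9.3 points at 12 months illustrates a 10% loss and nothing more.

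**What to change.** - Reword the first eligibility item in SAP 7.2.2 so that it flags only subjects who meet neither route of 2a: no documented NSCLC with Stage IIIB/IV disease, and no documented NSCLC that recurred or progressed after multimodal therapy.
- State that stage at initial diagnosis does not by itself trigger the deviation.
- Name the data fields used. Identify second-route subjects from the prior surgery, radiotherapy and systemic-therapy data already collected (SAP 7.3.4), and name the field that documents recurrence or progression.
- Use one term, *major* or *relevant*, in both 6.3 and 7.2.2.

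The cost is a short SAP edit and a small programming change before the analysis. It needs no protocol amendment and no added subjects.
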